13.2 CYCLOSPORINE (GENGRAF, SANDIMMUNE, NEORAL)

Supply: Cyclosporine will be obtained by the NIH Clinical Center Pharmacy Department from commercial sources and is available in capsules (25 mg and 100 mg), USP [MODIFIED], oral solution (100 mg/ml), USP [MODIFIED], and as a parenteral concentrate for injection (50 mg/ml). When oral capsules are prescribed for this protocol, the cyclosporine capsules, USP [NON-MODIFIED] should NOT be used.

Preparation: For parenteral doses, each milliliter of concentrate (50mg/ml) should be diluted in 20 to 100ml of dextrose 5% in water or sodium chloride 0.9%. Parenteral doses of cyclosporine will be prepared in non-PVC containers and infused with non-PVC administration sets/tubing. The recommended liquids for dilution of the oral solution to improve palatability include milk, chocolate milk or orange juice, preferable at room temperature.

Storage and Stability: Capsules, oral solution, and ampules of parenteral concentrate bear expiration dates and are stored at room temperature and protected from light. Cyclosporine concentrate for injection that has been diluted to a final concentration of approximately 2mg/ml is stable for 24 hours in 5% dextrose or 0.9% sodium chloride injection in glass, PVC or non-PVC plastic containers. To minimize the potential for sorption to PVC plastic bags and tubing as well the leaching of phthalate plasticizer (DEHP) into the solution, only non-PVC plastic bags and intravenous administration sets should be utilized.

Administration: Cyclosporine may be given intravenously or orally.

Toxicities: see section 12.4.2 Risks related to CsA

13.3 ANTI-THYMOCYTE GLOBULIN (EQUINE) STERILE SOLUTION (ATGAM®)

Other: Antithymocyte Gammaglobulin, Antithymocyte Globulin, ATGAM, Antithymocyte Immunoglobulin, lymphocyte immune globulin and h-ATG

Supply / availability: commercially available (Pharmacia & Upjohn Company)

Product description: Anti-thymocyte globulin (equine) sterile solution (ATGAM®) is available in 5 ml ampoules containing 50 mg of horse gamma globulin/mL (250 mg per ampoule).

Preparation: The calculated dose of anti-thymocyte globulin should be diluted in 0.9% sodium chloride injection to a concentration not to exceed 4 mg/mL.

Storage / stability: Anti-thymocyte globulin (equine) ampoules should be stored in a refrigerator at 2° to 8° C. Once diluted, anti-thymocyte globulin (equine) is physically and chemically stable for up to 24 hours at concentrations of up to 4 mg/mL in the recommended diluents. It is

Abbreviated Title: Early Initiation of Oral Therapy for Naïve Severe Aplastic Anemia (SAA)

Version Date: 11/05/2025

recommended that diluted anti-thymocyte globulin (equine) be stored in a refrigerator if it is prepared prior to the time of infusion.

Administration: Anti-thymocyte globulin (equine) should be administered into a high-flow central vein through an in-line filter with a pore size of 0.2 to 1 micron. The dose should be infused over no less than 4 hours. Infusion times may be extended to up to 24 hours for intolerance. Patients should be closely monitored for infusion / allergic reactions.

Compound: Principally monomeric IgG, prepared from plasma or serum of healthy horses hyperimmunized with human thymus lymphocytes.

Action: Immunosuppressive agent. Exact mechanism of immunosuppression of ATGAM has not been fully elucidated but may involve elimination of antigen-reactive T-cells in peripheral blood and/or alteration of T-cell function.

Side effects: see section 12.4.1 Risks related to h-ATG

13.4 PENTAMIDINE

Supply: Commercially available (NebuPent[®], American Pharmaceutical Partners, Inc.).

Product description: Pentamidineisethionate is available as a 300 mg single dose vial containing 300 mg of lyophilized powder in a 15 mL capacity vial. The contents of one vial must be dissolved in 6 mL of sterile water for injection, USP. It is important to use only sterile water; saline solution will cause the drug to precipitate.

Storage and stability: Store dry product at controlled room temperature 15-30⁰C (59-86⁰F).

Route of administration: Inhalation; Once reconstituted, the entire contents of a vial should be placed into the Respigard[®] II nebulizer (Marquest) reservoir for administration by inhalation. Do not mix the pentamidine solution with any other drugs.

Toxicities: see section 12.4.10 Risks related to Concomitant medications.

13.5 VALACYCLOVIR

Generic name: valacyclovir

Brand Name: Valtrex

Supply: Commercially available.

Pharmacology: Valacyclovir is the hydrochloride salt of L-valyl ester of the antiviral drug acyclovir. After oral administration, valacyclovir is rapidly absorbed from the GI tract and nearly completely converted to acyclovir and L-valine by first-pass intestinal or hepatic metabolism.

Product description: Valacyclovir is available in 500mg tablets and 1gm tablets. Dose adjustment is necessary in patients with significant renal impairment (refer to the manufacturer's labeling for dose adjustment guidelines).

Storage and Stability: Oral tablets should be stored at 15⁰ to 25⁰C (59⁰ to 77⁰F). **Route of administration:** Oral

Toxicities: see section 12.4.10 risks related to concomitant medications.

Abbreviated Title: Early Initiation of Oral Therapy for Naïve Severe Aplastic Anemia (SAA)

Version Date: 11/05/2025

APPENDIX A: GUIDE FOR LOCAL PHYSICIAN

1. CYCLOSPORINE (CsA)

- a. Dose: 2mg/kg daily by mouth
- b. Administration: To be taken consistently in relation to time of day and meals.
*Recommend taking it in the morning same time every day with food
- c. Supportive medication considerations:
 - i. Magnesium: Patients are expected to have magnesium wasting. Weekly labs should include magnesium levels and low levels need to be treated with magnesium supplementation (Goal >2mg/mL)
- d. Food/Medication interactions
 - i. Various agents are known interfere with plasma cyclosporine concentrations usually by inhibition or induction of CYP3A4
 - ii. Common drugs: Erythromycin, ketoconazole, diltiazem, rifampin, phenytoin, and phenobarbital. Refer to FDA label when prescribing new medications if unsure regarding possible interactions. Avoid using concomitantly with cyclosporine.
 - iii. Avoid Grapefruit juice and grapefruit
- e. Clinical and Laboratory monitoring
 - i. Common side effects: Headaches, hypertension, gastrointestinal upset, nausea. Posterior reversible encephalopathy syndrome (PRES) is a rare side effect.
*Recommend Amlodipine for hypertension (Goal <120/80mm/Hg)
*Recommend ondansetron and pantoprazole for nausea/GI upset
 - ii. Renal panel including magnesium at least weekly
 - iii. Cyclosporine level per investigators at NIH or local physician as clinically indicated only
- f. Dose Delays, Modifications or Discontinuation
 - i. **Discuss with investigators prior to dose alteration or discontinuation unless medically emergent. Please communicate any changes immediately.**
 - ii. Common reasons: renal impairment, severe gum hyperplasia, severe headaches, hyperkalemia

2. ELTROMBOPAG

- a. Dose:

Dosing according to age and ethnicity

Age groups (years)	Daily dose
Non-Asian	
12-85	150 mg
6-11	75 mg
2-5	2.5 mg/kg
East Asian, South East Asian	
12-85	75 mg
6-11	37.5 mg
2-5	1.25 mg/kg

b. Administration

- i. Take on empty stomach (1 hour before or 2 hours after a meal) or with food containing no calcium or dairy products
- ii. Allow at least 4-hour interval between eltrombopag and other medications containing polyvalent cations (e.g. calcium, magnesium, aluminum, zinc, selenium or iron)

*** RECOMMEND – EARLY MORNING (4-5AM) IF BREAKFAST PLANNED AFTER 7AM AND DINNER COMPLETED BEFORE MIDNIGHT**

c. Food/ Medication interactions

- i. Strong inhibitors of cytochrome p450 may enhance eltrombopag activity – recommend to not use it
- ii. Examples: Trimethoprim, ciprofloxacin, and gemfibrozil
- iii. Food: Dairy, calcium and other polyvalent cations (as listed above)

d. Clinical and laboratory monitoring

- i. Skin rash – typically severe diffuse drug rash
- ii. Complete blood counts and hepatic panel at least twice weekly x 2 weeks than weekly if clinically acceptable

e. Dose Delays, Modifications or Discontinuation (discuss with investigators immediately prior to making any changes)

- i. If ALT > 6 times ULN, repeat in 3 days Hold eltrombopag if ALT still >6 times ULN. Once ALT < 5 times ULN, restart eltrombopag at a dose level that is 25mg/day lower than the prior dose
- ii. Discontinue eltrombopag if deep venous thrombosis (other than a line related upper extremity thrombosis), pulmonary embolism, TIA/stroke, or myocardial infarction
- iii. Discontinue eltrombopag if diffuse skin rash
- iv. Decrease dose as follows for over correction of platelets

Platelet Count	Dose Adjustment or Response
>200,000/ μ L (untransfused) at any time on study	Decrease dosage by 25mg every 2 weeks to lowest dosage that maintains platelet count \geq 50,000/ μ L. In children under 12, the dose will be decreased by 12.5 mg.
>400,000/ μ L (untransfused) at any time on study	Discontinue eltrombopag for one week, if platelets fall to <200,000/ μ L; restart at dosage decreased by 25 mg/day (or 12.5 mg in children under 12).

3. Acceptable supportive treatment while on study

a. Blood and platelet transfusions

i. Platelet transfusions are recommended when:

1. PLT level is $<10 \times 10^9/L$, or
2. PLTs $<20 \times 10^9/L$ and with active bleeding, or
3. Per local standard of care (SOC), or as medically necessary.

ii. RBC transfusions are recommended when:

1. Hgb $<7 \text{ g/dL}$, or if symptomatic according to local SOC.
2. Infection management

b. Hematopoietic growth factors (e.g., G-CSF, GM-CSF, or erythropoietin) if deemed necessary. DO NOT ADMINISTER Romiplostim (N-Plate) or IL-11 (Neumega)

- c. Oral contraceptives or Leuprolide acetate for menses suppression
- d. Antibiotics, anti-fungals and anti-virals are permitted as clinically indicated. The local medical guidelines for treatment of infections/febrile neutropenia should be followed.

4. Laboratory monitoring for cytopenias

Abbreviated Title: Early Initiation of Oral Therapy for Naïve Severe Aplastic Anemia (SAA)

Version Date: 11/05/2025

- a. CBC weekly and reticulocyte (if testing available) weekly
- b. Transfusion goals: Hb >8g/dL or otherwise clinically indicated, plt >10 μ L or otherwise clinically indicated

5. Neutropenic fever management

- a. Single temperature of 38.5°C or two readings of 38.0°C or greater will need hospital admission to begin prompt broad-spectrum empiric antibiotics per current infectious disease guidelines. Full infectious work up required to identify source.
- b. Notify the NIH care team immediately

Contacts:

Please contact us if you have any questions or concerns about any of the above information.

The main point of contact is study coordinator [name]. She can be contacted at [contact] or emailed at [contact].

Other points of contact include:

Principal Investigator: [name]: Ph [contact], Email [contact]

Associate Investigator: [name]: Ph [contact], Email [contact]

Associate Investigator: [name]: Ph [contact], Email [contact]

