5.2 ELTROMBOPAG

Subjects will initiate EPAG at a starting daily dose as detailed in Table 3, according to age and ethnicity. Pediatric subjects between 12 and 17 years of age will receive the adult dose of 150 mg daily. Those between 6 and 11 will start at 75 mg, and children between 3 and 5 years of age will be started at 2.5 mg/kg (Table 1).

To adjust for the higher expected exposure in patients from East Asian and Southeast Asian ancestry, the starting dose for East Asian and Southeast Asian subjects between 12 and 85 years of age will be 75 mg once daily. For East Asian and Southeast Asian subjects between 6 and 11 years of age, the starting dose will be 37.5 mg once daily, and for children between 3 and 5, the starting dose will be 1.25 mg/kg (Table 3). EPAG will be administered orally as tablets or an oral suspension from sachet of EPAG powder. If an adult receives the oral suspension administration of EPAG, the required number of sachets will be used to administer the below adult doses. Detailed information about the supply and tablet/PfOS availability is in section 13.1.

Table 1. Dosing according to age and ethnicity

Age groups	Daily dose
Non-Asian	
12-85	150 mg
6-11	75 mg
3-5	2.5 mg/kg
East Asian, Southeast Asian	
12-85	75 mg
6-11	37.5 mg
3-5	1.25 mg/kg

EPAG may be taken on an empty stomach (1 hour before or 2 hours after a meal) or with food containing little (<50 mg) or preferably no calcium or dairy products. Allow at least a 4-hour interval between EPAG and other medications or products containing polyvalent cations (e.g. calcium, magnesium, aluminum, zinc, selenium or iron) such as antacids, dairy products, and mineral supplements to avoid significant (70-75%) reduction in eltrombopag absorption due to chelation.

EPAG dose may be interrupted when clinically indicated at the discretion of the investigator (for example if the patient is in the intensive care unit and unable to take PO medications).

Interruptions such as delays in request for medication refills or medication errors by subjects, or during circumstances such as COVID 19 pandemic that do not result in a serious adverse event or impact the integrity of the research data, will only be recorded in the medical record.

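### Appendix A and Sections 5.2 and 5.11 disagree on separating eltrombopag from dairy and other cation products, and Appendix A's recommended clock time guarantees only 2 to 3 of the 4 hours the protocol body asks for

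*Combined protocol and SAP*

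**What the plan says.** Section 5.2 gives two administration rules. The meal rule allows eltrombopag on an empty stomach, meaning 1 hour before or 2 hours after a meal, or with food containing little or no calcium. The cation rule is separate: "Allow at least a 4-hour interval between EPAG and other medications or products containing polyvalent cations". Its examples include antacids as well as "dairy products, and mineral supplements to avoid significant (70-75%) reduction in eltrombopag absorption due to chelation". Section 5.11, which sets out what subjects are told, repeats the 4-hour separation from antacids and other cation-containing products and again names dairy.

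Appendix A is the guide that Section 5.1 says will go to the outside physician. Its meal rule (item 2b.i) is "Take on empty stomach (1 hour before or 2 hours after a meal) or with food containing no calcium or dairy products". Its 4-hour rule (item 2b.ii) is narrower in scope than Section 5.2: "Allow at least 4-hour interval between eltrombopag and other medications containing polyvalent cations". Item 2c.iii names dairy, calcium and other cations as food interactions but gives no interval. The recommended time of day is "EARLY MORNING (4-5AM) IF BREAKFAST PLANNED AFTER 7AM AND DINNER COMPLETED BEFORE MIDNIGHT".

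Two other passages bear on the same morning. Appendix A item 1b says of cyclosporine: "Recommend taking it in the morning same time every day with food". Section 13.2 says that recommended "liquids for dilution of the oral solution to improve palatability include milk, chocolate milk or orange juice".

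**The concern.** The body of the protocol and the guide used off site give different versions of one instruction. A local physician working from Appendix A would see a 4-hour interval for medications, a warning about dairy with no interval, and a clock time that puts breakfast as little as 2 hours after the dose. Nothing in Appendix A says that a breakfast with dairy or calcium would have to come later.

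Early remote cyclosporine plus eltrombopag is the intervention under test, so consistent administration in the lead-in matters for reading the count changes before h-ATG (Section 2.3.7) and freedom from h-ATG (Section 9.2). Median time on oral therapy was 14 days (Section 2.3.7), so a daily breakfast habit could run through the whole lead-in. Section 7 counts failure to comply with the recommended oral treatment as non-compliance, and two versions of the recommendation make that standard less clear. The weekly call in Appendix B asks about medication compliance but has no item on timing relative to dairy or cations, and the Schedule of Events lists no eltrombopag level. A breach could go unrecorded.

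**Working it through.** The plan states no figure to reproduce. The check is clock arithmetic against the two rules.

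**Inputs**
- Dose at 4 to 5 AM, breakfast after 7 AM, dinner finished before midnight (Appendix A, recommended timing).
- Meal rule: 1 hour before or 2 hours after a meal (Sections 5.2 and 5.11; Appendix A 2b.i).
- Cation rule: at least 4 hours. It covers medications and products including dairy in Sections 5.2 and 5.11, and medications only in Appendix A 2b.ii.

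**Morning side.** Gap = breakfast time − dose time.

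| Dose | Breakfast | Gap | At least 1 h before meal | At least 4 h, if breakfast has dairy or calcium |
|---|---|---|---|---|
| 4:00 | 7:00 | 3 h | met | not met |
| 4:00 | 8:00 | 4 h | met | met |
| 4:30 | 7:00 | 2.5 h | met | not met |
| 4:30 | 8:30 | 4 h | met | met |
| 5:00 | 7:00 | 2 h | met | not met |
| 5:00 | 9:00 | 4 h | met | met |

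Breakfast is to be after 7 AM, so 3 h and 2 h are minimum gaps.

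The earliest breakfast with dairy or calcium that satisfies Sections 5.2 and 5.11 is dose time + 4 h: 4:00 + 4 h = 8:00, and 5:00 + 4 h = 9:00. The conflict window is therefore 7:00 to 8:00 for a 4 AM dose and 7:00 to 9:00 for a 5 AM dose.

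**Evening side.** Dinner finished by midnight leaves at least 4 − 0 = 4 h (4 AM dose) or 5 − 0 = 5 h (5 AM dose). Both the 2-hour and the 4-hour rules are met.

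**Scope of the 4 hours, side by side**
- Sections 5.2 and 5.11: medications and other products, with dairy and mineral supplements named.
- Appendix A 2b.ii: medications.
- Appendix A 2c.iii: dairy and calcium named, no interval, with a pointer back to the list above.

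If that pointer is read as carrying the 4 hours over to dairy, the recommended clock time can breach Appendix A's own rule. If it is not, Appendix A is narrower than Sections 5.2 and 5.11. The passages conflict on either reading.

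**The case against.** The best defence is that the clock time is about meals, and it meets the meal rule in all three places: every combination leaves at least 1 hour before breakfast and at least 2 hours after dinner. Section 5.11 also first presents the empty stomach and the low-calcium diet with a 4-hour separation as alternatives, and the clock time meets the first. This stands as far as it goes. For a breakfast free of dairy, calcium and other cations there is no conflict. The next paragraph of Section 5.11 and the second rule in Section 5.2 nevertheless require 4 hours from dairy as well.

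Dairy is not absent from Appendix A: item 2b.i excludes dosing with food containing it and item 2c.iii flags it. Only its interval is missing. Subjects are also to be advised directly under Section 5.11, which reduces the risk but leaves patient and physician with different instructions.

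A reader might add that magnesium supplements for cyclosporine fall inside the window. The documents do not support that: Appendix A 2b.ii names magnesium in its 4-hour rule, and Section 5.9 also keeps magnesium apart from eltrombopag. Taking cyclosporine with food is not itself a cation source, and the milk diluent concerns only users of the oral solution.

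A reader might also infer that patients lose most of the dose, reasoning that 150 × (1 − 0.70) = 45 mg or 150 × (1 − 0.75) = 37.5 mg is all that remains. The documents do not show this. Section 5.2 gives 70-75% as the reason for the interval, and Section 5.11 ties 70% to co-administration with antacids. Neither gives a loss for dairy eaten 2 to 3 hours after the dose. A link to clonal evolution is likewise unsupported.

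**Conclusion.** The inconsistency is real and limited. Appendix A drops the 4-hour interval for dairy and other non-medication products. Its clock time guarantees 2 to 3 hours where Sections 5.2 and 5.11 ask for 4, so it can be followed while breaching those sections.

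The breach depends on two conditions: breakfast contains dairy, calcium or another polyvalent cation, and it is eaten before 8 AM (4 AM dose) or 9 AM (5 AM dose). How many patients meet both is not in the documents and could be anywhere from few to most. Reduced eltrombopag absorption is possible on affected days, but its size cannot be stated. No sample size, power or primary-endpoint figure changes. The finding also does not show which passage is mistaken. It shows only that they disagree.

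**What to change.** Reconcile Sections 5.2 and 5.11 with Appendix A items 2b and 2c and the recommended clock time, so that the products covered by the 4-hour interval and the dosing and breakfast times agree everywhere. Then check that the morning cyclosporine-with-food advice in Appendix A item 1b and the milk diluent in Section 13.2 fit the reconciled rule. The sponsor must decide which timing stands; this review proposes none. The cost is revised wording, chiefly in the appendix, with no new procedures or visits.

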5.4.2 Liver function abnormalities

Eltrombopag dose may be interrupted when clinically indicated at the discretion of the investigator. Recommend dose modifications for isolated ALT or AST elevation according to the following rules:

Isolated ALT or AST elevation	Dose modification
>ULN – 3.0 x ULN	Maintain dose level
>3.0 – 5.0 x ULN	Maintain dose level. Repeat liver function tests as soon as possible, preferably within 48-72 hours, from awareness of the abnormal results. If abnormal laboratory values are confirmed upon the repeat test, monitor liver function tests weekly or more frequently if clinically indicated until resolved to ≤3.0 x ULN .
>5.0 – 10.0 x ULN	Interrupt dose. Repeat liver function tests as soon as possible; preferably within 48-72 hours from awareness of the abnormal results. Monitor liver function tests weekly, or more frequently if clinically indicated until resolved to ≤3.0 x ULN then: If resolved in ≤14 days, maintain dose level. If resolved >14 days, decrease one dose level
>10.0-20.0 x ULN	Interrupt dose. Repeat liver function tests as soon as possible, preferably within 48-72 hours from awareness of the abnormal results. Monitor liver function tests weekly, or more frequently if clinically indicated until resolved to baseline . Then decrease one dose level.
>20.0 ULN	Discontinue subject from study drug treatment. Repeat liver function tests as soon as possible, preferably within 48-72 hours from awareness

Isolated ALT or AST elevation	Dose modification
	of the abnormal results. Monitor liver function tests weekly or more frequently if clinically indicated until resolved to baseline or stabilization over 4 weeks.

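### Appendix A gives local physicians an eltrombopag liver rule that conflicts with the table in section 5.4.2, and nothing says which one governs

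*Combined protocol and SAP*

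**What the plan says.** Section 5.4.2 is worded as advice: "Recommend dose modifications for isolated ALT or AST elevation according to the following rules". It also leaves room for judgement: "Eltrombopag dose may be interrupted when clinically indicated at the discretion of the investigator". Its table keeps the dose up to 5 × ULN. In the row above 5 and up to 10 × ULN the instruction is "Interrupt dose. Repeat liver function tests as soon as possible; preferably within 48-72 hours from awareness of the abnormal results". The drug stays off until 3 × ULN or lower; then "If resolved in ≤14 days, maintain dose level", otherwise one level lower. In the row above 10 and up to 20 × ULN the interruption lasts until baseline: "Then decrease one dose level". Above 20 × ULN: "Discontinue subject from study drug treatment".

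Section 5.1 says Appendix A goes to the outside physician as a guide to dosing, adverse events and monitoring. Its item 2.e.i reads "If ALT > 6 times ULN, repeat in 3 days Hold eltrombopag if ALT still >6 times ULN", followed by "Once ALT < 5 times ULN, restart eltrombopag at a dose level that is 25mg/day lower than the prior dose". It names ALT only and has no further tier. The heading of 2.e asks the physician to speak to the investigators before changing anything. Item 2.d.ii asks for hepatic panels twice weekly for two weeks; section 6.2 asks for them at least weekly.

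The nearest thing to a ranking is in section 5.9, which sends the reader to 5.4 only for liver abnormalities caused by an eltrombopag–cyclosporine interaction.

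**The concern.** The same laboratory result leads to different actions depending on which page is open. The physician who sees a remotely treated patient's result works from Appendix A. In most respects that page acts later and restarts sooner than the protocol body. At ALT between 5 and 6 × ULN, or when only AST is raised, it gives no instruction at all, although section 6.2 records both enzymes off site.

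What is at stake is patient safety and consistent dosing during the oral period. The extension cohort adds 41 patients under the same design, so the guide will continue to be used.

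**Working it through.** The protocol gives no figure to reproduce. The check applies each rule to the same values. The values are illustrative, and bilirubin is assumed normal so that the rise counts as isolated.

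| First result (× ULN) | Section 5.4.2 | Appendix A 2.e.i |
|---|---|---|
| ALT 4, AST 2 | Keep dose, repeat in 48–72 h | No instruction (same dose) |
| ALT 5.5, AST 4 | Interrupt | No instruction |
| ALT 8, AST 4 | Interrupt; resume at 3 or lower | Repeat at 3 days; hold only if still above 6; restart below 5, 25 mg lower |
| ALT 15, AST 10 | Interrupt to baseline, then one level lower | Same as at ALT 8 |
| ALT 25, AST 15 | Discontinue | Same as at ALT 8 |
| ALT 4, AST 8 | Interrupt | No instruction |
| ALT 3, AST 12 | Interrupt to baseline, then one level lower | No instruction |

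Below 5 × ULN the dose is the same under both. Above 5 × ULN the two differ in 6 of 6 examples. They also differ on recovery: if ALT has fallen from 8 to 4.5 × ULN during a hold, 5.4.2 keeps the drug off and Appendix A restarts it.

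**Direction of the differences.** Appendix A is less cautious on five counts:
- enzyme: ALT only, against ALT or AST;
- hold level: above 6, against above 5;
- hold timing: after a confirming repeat, against at once;
- restart level: below 5, against 3 or lower (or baseline);
- upper tiers: none, against two.

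It is stricter on two. The restart dose is always lower, whereas 5.4.2 allows the same dose if the rise resolves within 14 days. Early panels are twice weekly for two weeks.

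**Extra exposure above 6 × ULN.** Eltrombopag is taken once daily and the repeat is at 3 days. The excess is 0 doses if the NIH team acts on the first result and 3 if dosing runs to the repeat.

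**Dose step (minor).** The flat 25 mg step has no paediatric version, although the platelet rules in section 5.3 and Appendix A use 12.5 mg under age 12. For East or Southeast Asian children aged 3–5 the starting dose is 1.25 mg/kg:
- at 20 kg, 1.25 × 20 = 25 mg, and 25 − 25 = 0 mg;
- at 12.1 kg, just above the weight limit, 1.25 × 12.1 = 15.1 mg, and 15.1 − 25 = −9.9 mg.

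A 12.5 mg step leaves 12.5 mg and 2.6 mg respectively, so children dosed by weight need their own step. The case is rare: in Table 1 of section 2.3.7 the youngest of the first 36 patients was 8, and 2 of 36 were Asian.

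**The case against.** The strongest reply is that the local physician does not decide alone. The synopsis and section 6.2 place remote treatment under the full guidance of the NIH team. Laboratory results are requested for the research nurse, the weekly call in Appendix B reviews liver tests, and changes are discussed first. Section 9.6 separately stops the drug for grade IV events probably or definitely related to eltrombopag and for persistent hepatotoxicity. The oral period is short: section 2.3.7 gives a median of 14 days (range 0 to 86), so at the median the twice-weekly panels span the whole course. Section 5.4.2 is itself discretionary. Section 2.3.3 reports fewer liver abnormalities with cyclosporine plus eltrombopag for relapse (unpublished), and section 12.3.3 places isolated severe liver injury at about three months.

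Most of this stands and limits the risk, but it does not reconcile the rules. The discuss-first step is triggered by a change, and at 5–6 × ULN or for an AST-only rise Appendix A asks for none. Panels can drop to every two weeks at the investigator's discretion. Section 9.6 is not on the physician's page, and it defines persistent hepatotoxicity by a section 6.4.2 that does not appear in the text. Eight weeks is a ceiling that can be extended by 4 weeks, or to 6 months in special circumstances. Two discretionary recommendations that contradict each other are still contradictory.

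A reader might infer that Appendix A orders dosing to continue for three days, or that a patient with ALT above 20 × ULN would be restarted unchecked. Neither is supported. Continued dosing is implied by the order of the steps rather than stated, and NIH review and section 9.6 stand between such a patient and a restart.

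**Conclusion.** The inconsistency is real and should be fixed. Appendix A and section 5.4.2 conflict on enzyme, hold level, restart level and upper tiers, and no general statement says which prevails. Because the guide mostly holds later and restarts earlier than the protocol body, this is a safety defect in the document and not just missing detail. Confidence is high, since it rests on the wording alone.

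Its size is modest: at most three extra daily doses above 6 × ULN while a repeat is awaited, no prompt in the two gaps described, and a restart at a higher enzyme level but a lower dose.

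Two broader inferences are not supported. One is that patients were harmed or that liver events are frequent: the documents give no rate of ALT or AST above 5 × ULN on early oral therapy, and their evidence on frequency points both ways. The other is that the primary endpoint is affected: section 2.3.7 reports 0 composite events after 36 subjects, and nothing here touches the sample size or analysis. Nor is Appendix A laxer throughout.

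**What to change.** - Replace Appendix A 2.e.i with the 5.4.2 table for ALT or AST, including the two upper tiers. The twice-weekly early panels can stay.
- State in both places that 5.4.2 governs.
- Tell local physicians to contact the NIH team whenever a 5.4.2 action threshold is met, whether or not they plan a change.
- Correct the section 9.6 reference from 6.4.2 to 5.4.2.
- Define the dose step, since 5.4.2 speaks of one level without giving its size: 12.5 mg under age 12, as in 5.3, in place of a flat 25 mg, and a workable step chosen by the sponsor for children dosed by mg/kg.
- Re-send Appendix A to the physicians of patients now on oral therapy.

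The cost is one replaced rule, a few sentences and a mailing. Design, sample size and analysis do not change.
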